#### 5.2.6.1.2 Serious adverse event

A serious adverse event (SAE) is defined as any AE, which fulfils at least one of the following criteria:

- results in death,
- is life-threatening, which refers to an event in which the patient was at risk of death at the time of the event; it does not refer to an event that hypothetically might have caused death if more severe,
- requires inpatient hospitalisation or prolongation of existing hospitalisation
- results in persistent or significant disability or incapacity,
- is a congenital anomaly / birth defect,
- is deemed serious for any other reason if it is an important medical event when based on appropriate medical judgement which may jeopardise the patient and may require medical or surgical intervention to prevent one of the other outcomes listed in the above definitions. Examples of such events are intensive treatment in an emergency room or at home for allergic bronchospasm, blood dyscrasias or convulsions that do not result in hospitalisation or development of dependency or abuse.

For Japan only: the following events will be handled as “deemed serious for any other reason”. AEs which possibly lead to disability will be reported as SAEs.

Patients may be hospitalized for administrative reasons during the trial, including hospitalisation for respite care. These as well as hospitalisations/surgical procedures which

Proprietary confidential information © 2020 Boehringer Ingelheim International GmbH or one or more of its affiliated companies

were planned before the patient signed informed consent need not be reported as SAEs if they have been documented at or before signing of the informed consent and have been performed as planned (the condition requiring hospitalisation/surgical procedure has not changed/worsened after signing informed consent)

#### 5.2.6.1.3 AEs considered “Always Serious”

In accordance with the European Medicines Agency initiative on Important Medical Events, Boehringer Ingelheim has set up a list of AEs, which by their nature, can always be considered to be “serious” even though they may not have met the criteria of an SAE as defined above.

The latest list of “Always Serious AEs” can be found in the electronic data capture (eDC) system. A copy of the latest list of “Always Serious AEs” will be provided upon request. These events should always be reported as SAEs as described in [section 5.2.6.2](#). Every new occurrence of cancer of new histology must be classified as a serious event regardless of the time since the discontinuation of the trial medication and must be reported as described in section 5.2.6.2, subsections “**AE Collection**” and “**AE reporting to sponsor and timelines**”.

#### 5.2.6.1.4 Adverse events of special interest

The term adverse events of special interest (AESI) relates to any specific AE that has been identified at the project level as being of particular concern for prospective safety monitoring and safety assessment within this trial, e.g. the potential for AEs based on knowledge from other compounds in the same class. AESIs need to be reported to the sponsor’s Pharmacovigilance Department within the same timeframe that applies to SAEs, please see [section 5.2.6.2.2](#).

The following are considered as AESIs:

##### **Dose-limiting toxicities**

DLTs are considered to be AESIs, and must be reported as such. The definition of DLTs is presented in [Section 5.2.6.3](#).

##### **Potential severe drug-induced liver injury (DILI)**

A potential severe Drug Induced Liver Injury (DILI) that requires follow-up is defined by the

➤ following alterations of hepatic laboratory parameters: For patients with normal aminotransaminase levels at baseline:

- An elevation of AST and/or ALT  $\geq 3$  fold ULN combined with an elevation of total bilirubin  $\geq 2$  fold ULN either measured in the same blood draw sample, or in samples drawn within 30 days of each other; or
- Aminotransferase (ALT and/or AST) elevations  $\geq 10$  fold ULN.

• For patients with abnormal aminotransaminase levels between  $>1$  and  $<3 \times$  ULN at baseline:

Proprietary confidential information © 2020 Boehringer Ingelheim International GmbH or one or more of its affiliated companies

- An elevation of AST and/or ALT  $\geq 3$  fold the baseline value combined with an elevation of bilirubin  $\geq 2$  fold ULN or  $\geq 2$  fold the baseline value (if bilirubin is elevated at baseline) in the same blood sample, or in samples drawn within 30 days of each other ; or
- Aminotransferase elevations  $\geq 5$  fold the baseline value.

- For patients with abnormal aminotransaminase levels between  $\geq 3$  and  $\leq 5$  x ULN at baseline:
  - An elevation of AST and/or ALT  $\geq 2$  fold the baseline value combined with an elevation of bilirubin  $\geq 2$  fold ULN or  $\geq 2$  fold the baseline value (if bilirubin is elevated at baseline) in the same blood sample, or in samples drawn within 30 days of each other; or
  - Aminotransferase elevations  $\geq 3$  fold the baseline value.

These lab findings constitute a potential hepatic injury alert and the patients showing these lab abnormalities need to be followed up according to the “DILI checklist” provided in the ISF. For further details, see figure 5.2.6.1.4: 1 below.

[figure not shown]

Figure 5.2.6.1.4: 1 Hepatic injury reporting

#### 5.2.6.1.5 Intensity (severity) of AEs

The intensity (severity) of adverse events should be classified and recorded in the CRF according to the CTCAE version 5.0 ([R18-1357](#)).

#### 5.2.6.1.6 Causal relationship of AEs

Medical judgement should be used to determine whether there is a reasonable possibility of a causal relationship between the adverse event and the given study treatment, considering all

Proprietary confidential information © 2020 Boehringer Ingelheim International GmbH or one or more of its affiliated companies

relevant factors, including pattern of reaction, temporal relationship, de-challenge or re-challenge, confounding factors such as concomitant medication, concomitant diseases and relevant history.

Arguments that may suggest that there is a reasonable possibility of a causal relationship could be:

- The event is consistent with the known pharmacology of the drug.
- The event is known to be caused by or attributed to the drug class.
- A plausible time to onset of the event relative to the time of drug exposure.
- Evidence that the event is reproducible when the drug is re-introduced.
- No medically sound alternative aetiologies that could explain the event (e.g. pre-existing or concomitant diseases, or co-medications).
- The event is typically drug-related and infrequent in the general population not exposed to drugs (e.g. Stevens-Johnson syndrome).
- An indication of dose-response (i.e. greater effect size if the dose is increased, smaller effect size if dose is reduced).

Arguments that may suggest that there is no reasonable possibility of a causal relationship could be:

- No plausible time to onset of the event relative to the time of drug exposure is evident (e.g. pre-treatment cases, diagnosis of cancer or chronic disease within days / weeks of drug administration; an allergic reaction weeks after discontinuation of the drug concerned).
- Continuation of the event despite the withdrawal of the medication, taking into account the pharmacological properties of the compound (e.g. after 5 half-lives). Of note, this criterion may not be applicable to events whose time course is prolonged despite removing the original trigger.
- Additional arguments amongst those stated before, like alternative explanation (e.g. situations where other drugs or underlying diseases appear to provide a more likely explanation for the observed event than the drug concerned).
- Disappearance of the event even though the trial drug treatment continues or remains unchanged.

### 5.2.6.2 Adverse event collection and reporting

#### 5.2.6.2.1 AE Collection

The investigator shall maintain and keep detailed records of all AEs in the patient files. The following must be collected and documented on the appropriate CRF(s) by the investigator:

- From signing the informed consent onwards until the EOR all AEs (non-serious and serious) and all AESIs.
- After EOR until the individual patient's end of trial:  
cancers of new histology and exacerbations of existing cancer, all trial treatment related SAEs and all trial treatment related AESIs.

Proprietary confidential information © 2020 Boehringer Ingelheim International GmbH or one or more of its affiliated companies

- After the individual patient's end of the trial: the investigator does not need to actively monitor the patient for new AEs but should report any occurrence of cancer and trial treatment related SAEs and trial treatment related AESIs of which the investigator may become aware of by any means of communication, e.g. phone call. Those AEs should be reported on the BI SAE form (see section 5.2.6.2.2), but not on the CRF.

The rules for Adverse Event Reporting exemptions still apply, please see [section 5.2.6.2.4](#).

#### Vital Status Data Collection

Patients who discontinue trial medication prematurely, who agree to be contacted further but do not agree to physical visits, should be followed up as described in [section 3.3.4.1](#), withdrawal from trial treatment. From then on until the individual patient's end of the trial the investigator must report all deaths/fatal AEs regardless of relationship, and trial treatment related SAEs and trial treatment related AESIs the investigator becomes aware of.

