- i) Tumour assessments should be done according to RECIST v1.1 and should include computed tomography (CT) scans of the chest and abdomen and, if clinically indicated, imaging of any other known or suspected sites of disease (e.g., pelvis, brain) using an appropriate method (CT scan or magnetic resonance imaging [MRI]). See [Section 5.1](#) for detail.
- j) PK sample (plasma [REDACTED]) will be collected at timepoint indicated in [Table 10.1: 1](#).  
k) [REDACTED]
- l) Archival formalin-fixed paraffin-embedded (FFPE) tumour tissue from most recent timepoint (preferred less than 6 month old) should be collected. See Section 5.4 and [Table 5.4.1: 1](#) for further details.
- m) BI 3011441 intake is daily. Dosing of BI 3011441 will be determined by the SMC and communicated separately as each new cohort opens for recruitment.
- n) DLTs will be collected throughout the trial and will be assessed for dose-escalation decisions following the first cycle. All serious adverse events (SAEs) and adverse events of special interest (AESIs) considered trial treatment related, cancers of new histology and exacerbations of existing cancer (see [section 5.2.6.2.1](#)) must be collected in the extended follow-up period.
- o) Patients who discontinue trial treatment prematurely and have agreed to be contacted, should be called at least at the end of their scheduled trial participation to obtain their vital status information, please see [Section 5.2.6.2.1](#)
- p) Before initiating a new treatment cycle, criteria should be checked, please see [Section 4.1.4.1](#)
- q) An EOT visit should be performed for all patients who permanently discontinued trial medication. If the decision to permanently discontinue treatment is taken at a scheduled visit, the EOT visit should be performed instead of the scheduled visit (preferably within 7 days after the last treatment).
- r) Residual effect period (REP) starts after last dose of trial medication and ends 30 days later. Whenever possible, a 30-day safety FU visit should take place before any other anti-cancer treatment starts.

Proprietary confidential information © 2020 Boehringer Ingelheim International GmbH or one or more of its affiliated companies

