#### 2.1.3 Secondary endpoint(s)

- Number of patients with DLTs during the entire on-treatment period
- Number of patients with Grade  $\geq 3$  treatment-related adverse events
- Number of patients with treatment related adverse events at each dose level
- Pharmacokinetic parameters of BI 3011441:  $C_{max(ss)}$ , and  $AUC_{0-tz(ss)}$

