### **3.3.4.1 Discontinuation of trial treatment**

An individual patient will discontinue trial treatment if:

- The patient wants to discontinue trial treatment, without the need to justify the decision.
- The patient has repeatedly shown to be non-compliant with important trial procedures and, in the opinion of both, the investigator and sponsor representative, is not willing or able to adhere to the trial requirements in the future.
- The patient needs to take concomitant medication that interferes with the investigational medicinal product or other trial treatment
- The patient becomes pregnant. The patient can no longer receive trial treatment for medical reasons (such as surgery, adverse events or other diseases).

BI 3011441 should be permanently discontinued in case of :

- Retinal vein occlusion (RVO)
- Symptomatic heart failure
- Interstitial lung disease/pneumonitis, regardless of grade
- Recurrent Grade 4 AEs or persistent Grade 2 to 3 AEs that do not recover to Grade 1 or less within 12 weeks
- Drug-related Grade 4 AEs.

An interruption of treatment or delayed start of treatment of more than 4 weeks or several interruptions exceeding a total of  $\geq 28$  days of BI 3011441 treatment due to SAEs/AEs will lead to permanent treatment discontinuation. However in well-justified cases if considered clinically indicated by the Investigator and aligned with the Sponsor (to be documented in writing), a patient can be re exposed to treatment.

In case of a temporary reason, trial treatment should be restarted if medically justified, please see [section 4.1.4](#).

If new efficacy/safety information of BI 3011441 becomes available, Boehringer Ingelheim (BI) will review the benefit-risk-assessment and, if needed, pause or discontinue the trial treatment for all patients or take any other appropriate action to guarantee the safety of the trial patients.

Even if the trial treatment is discontinued, the patients remain in the trial and, given their agreement, will undergo the procedures for early treatment discontinuation and follow-up as outlined in the [Flow Chart](#) and [section 6.2.3](#).

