### 7.3.5 Safety analyses

Adverse events will be coded using the Medical Dictionary for Drug Regulatory Activities (MedDRA). Standard BI summary tables and listings will be produced. All adverse events with an onset between start of treatment and end of the residual effect period (REP), a period of 30 days after the last dose of trial medication, will be assigned to the on-treatment period for evaluation.

All treated patients will be included in the safety analysis. In general, safety analyses will be descriptive in nature and will be based on BI standards. No hypothesis testing is planned.

Statistical analysis and reporting of adverse events will concentrate on treatment-emergent adverse events, i.e. all adverse events occurring between start of treatment and end of the REP ([Section 1.2](#)) Adverse events that start before first drug intake and deteriorate under treatment will also be considered as 'treatment-emergent'.

Frequency, severity, and causal relationship of adverse events will be tabulated by system organ class and preferred term after coding according to the current version of the MedDRA at database lock.

Laboratory data will be analyzed both quantitatively as well as qualitatively. The latter will be done via comparison of laboratory data to their reference ranges. Values outside the reference range as well as values defined as clinically relevant will be summarised. Treatment groups will be compared descriptively with regard to distribution parameters as well as with regard to frequency and percentage of patients with abnormal values or clinically relevant abnormal values.

Vital signs, physical examinations, or other safety-relevant data observed at screening, baseline, during the course of the trial and at the end-of-trial evaluation will be assessed with regard to possible changes compared to findings before start of treatment.

Other safety analyses (AESIs, centrally evaluated ECG, etc.) will be specified in detail in the TSAP.

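### Protocol 5.2.6.2.1 gives two AE collection rules for patients who stop drug early and decline visits; if the narrower rule is followed, two related-AE endpoints can only be biased downward

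*Protocol*

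**What the plan says.** The general rule in Protocol 5.2.6.2.1 requires the investigator to collect and document "From signing the informed consent onwards until the EOR all AEs (non-serious and serious) and all AESIs". It makes no exception for patients who decline visits.

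Under the same section number, the paragraph on vital status deals with patients who stop trial medication prematurely, "who agree to be contacted further but do not agree to physical visits". For them it states "From then on until the individual patient's end of the trial the investigator must report all deaths/fatal AEs regardless of relationship", together with "trial treatment related SAEs and trial treatment related AESIs the investigator becomes aware of". It refers to section 3.3.4.1, which says that "the patients remain in the trial and, given their agreement, will undergo the procedures for early treatment discontinuation and follow-up" but sets no remote AE schedule. Footnote o of the Flow Chart says that patients who stop prematurely and agree to contact "should be called at least at the end of their scheduled trial participation to obtain their vital status information".

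On the analysis side, Protocol 7.3.5 says that events with onset from the start of treatment to 30 days after the last dose "will be assigned to the on-treatment period for evaluation". SAP 6.1, 7.8 and 7.8.1.2 use the same window. Among the secondary endpoints in Protocol 2.1.3 are "Number of patients with treatment related adverse events at each dose level" and the number with related Grade 3 or higher events. Neither requires seriousness.

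**The concern.** Two rules apply to the same patients over the same 30 days. One asks for every AE. The other lists deaths and fatal AEs, related SAEs and related AESIs, and takes effect when the patient leaves drug and visits, not at EOR. A site that works from the second rule has no prompt to ask about related non-serious events in a period that the analysis treats as fully observed.

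The SAP would not show the gap. AE tables count patients (SAP 7.8.1.2), percentages are taken over all patients in the set whether or not they have non-missing values (SAP 7), and missing data are not imputed (SAP 6.6). A patient with shortened collection therefore stays in the denominator and looks the same as a patient who was followed and had no event. At stake is whether the related-AE counts by dose can be taken as complete in a trial of about 12 patients. The error would favour the drug.

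**Working it through.** The documents state no figure on this point, and Protocol 7.6 says that no power calculation was made, so there is nothing to reproduce. The check compares the two rules with the analysis window and then gives a scale.

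**1. The windows**
- General rule: consent to EOR, all AEs.
- Vital status rule: from discontinuation with visits declined to the patient's end of trial, reduced list, no exception for the residual effect period.
- Analysis: first dose to last dose + 30 days, all AEs.

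The general rule matches the analysis. The vital status rule leaves up to 30 days of the analysis window with narrower collection.

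**2. Events outside the reduced list.** An event must be related, non-serious, not an AESI, and start after the last dose. DLTs are AESIs (Protocol 5.2.6.1.4) and stay reportable, as do related SAEs and related liver-injury AESIs. What remains is mainly related Grade 1–2 events, and Grade 3 or higher events that section 5.2.6.3 excludes from DLT status if they are also non-serious. Examples are Grade 3 nausea or vomiting that does not persist beyond 48 hours, or Grade 3 diarrhoea without hospitalisation.

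**3. Patients affected.** Because patients are counted, a patient is lost from an endpoint only if the missed event is that patient's first qualifying one. A patient with a related AE already recorded on drug stays in the any-related-AE count, but could still be missed for Grade 3 or higher.

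**4. Share of the window after the last dose**, 30/(T + 30), for T days on drug:
- T = 7: 30/37 = 81%
- T = 14: 30/44 = 68%
- T = 28: 30/58 = 52%
- T = 56: 30/86 = 35%
- T = 112: 30/142 = 21%

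These are shares of time, not of events.

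**5. Effect of one missed patient on a cohort proportion.** With 3 or 6 patients: 1/3 = 33 points, 1/6 = 17 points. A patient who stops in Cycle 1 for a reason other than a DLT may be replaced (Protocol 3.3.4.1.2) but stays in the safety evaluations (SAP 7.8). With one replacement the denominators become 4 and 7: 1/4 = 25 points, 1/7 = 14 points. The range is 14 to 33 points.

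**6. Number of patients missed.** Let q be the share of patients who stop early and decline visits but accept contact. Let u be the chance that such a patient's only qualifying event falls in the gap. Both are assumptions; the documents give neither. With N = 12, the expected number missed is 12qu and P(at least one) = 1 − (1 − qu)^12.
- q = 5%, u = 10%: 0.06 patients; 6%
- q = 10%, u = 25%: 0.3 patients; 26%
- q = 20%, u = 25%: 0.6 patients; 46%
- q = 30%, u = 50%: 1.8 patients; 86%

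**The case against.** The strongest reply is that the vital status paragraph does not suspend the general rule. It never says that its list is exhaustive, it speaks of reporting where the general rule speaks of collecting on the CRF, and its list resembles what the general rule asks for after EOR, with all deaths added. On that reading it is a minimum for patients who no longer attend, and all AEs to EOR are still due.

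This reading is possible, and it means that a deliberate decision to stop collecting AEs cannot be inferred. But before EOR everything on the list is already required by the general rule, so on that reading the paragraph adds nothing in those 30 days. Two readings remain, and sites may differ.

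The other replies limit the size, and they stand. Events starting on drug are still collected. A related AE that would require permanent discontinuation is itself a DLT (Protocol 5.2.6.3). Known AEs are followed until resolved, chronic or stable, or until no further information can be obtained (Protocol 5.2.6.2.2). All analyses are descriptive.

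A reader might also infer that patients who tolerate the drug worst leave and take their events with them. That is plausible but not documented, and the toxicity that drives a patient off drug normally starts before the last dose, so it is captured. Nor does a large share of time after the last dose mean an equal share of lost events.

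**Conclusion.** The concern holds as an inconsistency between two rules in Protocol 5.2.6.2.1, with a conditional downward risk for two secondary endpoints: patients with related AEs, and patients with related Grade 3 or higher AEs. That these endpoints will be under-counted does not follow. It requires a site to apply the narrower rule and a patient whose first qualifying event is related, non-serious, not an AESI and starts after the last dose.

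The size cannot be computed from the documents. Over the assumed values of q and u the expected loss runs from 0.06 to 1.8 patients, so zero to two of about 12 is a reasonable judgement. The shift of 14 to 33 points applies per affected patient at cohort sizes of 3 to 7 and is not an expected bias.

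A reader might infer that the MTD is compromised. The documents do not support that: DLTs stay reportable as AESIs, so neither the primary DLT/MTD endpoint nor the DLT secondary endpoint loses an event by rule. Ascertainment does become more passive, since the paragraph relies on what the investigator learns. The point deserves correction because the remedy is cheap and the tables as planned would not reveal the gap.

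**What to change.** In the vital status paragraph of Protocol 5.2.6.2.1, state that all AEs, with grade and causality, are collected until last dose + 30 days, by telephone if visits are declined, and that the reduced list applies only after EOR. For a patient who attends no EOR visit, last dose + 30 days should stand as that date. Footnote o of the Flow Chart should refer to the telephone contact in this period.

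In the SAP, flag in the related-AE tables each patient whose AE collection ended before last dose + 30 days, so that incomplete observation can be told apart from absence of events.

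The cost is one sentence in the protocol, a flag in the tables, and one or two calls for a few patients who have already agreed to be contacted. Telephone contact will not recover abnormalities found only by laboratory test or examination; the flag covers that remainder. No sample size or dose-escalation figure changes.
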